To assess whether there are systematic differences between those who drop out and those who do not – and thus whether these factors should be included in analysis – we will model missingness at follow-up (defined as pupils with missing primary outcome data at endline) as a function of baseline covariates, including treatment. The analysis model for this approach will mirror the multilevel level model specified in Equation (1), with pupils clustered in classes, but the outcome will be a binary variable identifying missingness (where 1=missing; 0=complete) in a multilevel mixed-effects logistic regression model (using Stata's `meLogit` command). We can similarly model missingness at baseline (defined as pupils with missing baseline data, namely missing EYFSP) as a function of endline covariates, including treatment.

We will follow the protocol for missing data suggested by the EEF (see EEF, 2018). For less than 5% missingness overall from randomisation to final analysis, a complete-case analysis will be employed. This assumes that data are missing completely at random (MCAR), which we will be able to test partially with the model outlined above. For more than 5% missing data overall from randomisation to final analysis, our approach will depend on pattern of missingness. If the pattern of missingness may be unrelated to the treatment effect (e.g., pupil illness, staff changes or COVID-related impacts on testing but not on intervention), then missing data will be assumed MCAR and we will continue with a complete-case analysis. Otherwise, we will adopt a full-information maximum likelihood (FIML) approach. FIML estimates the value of the trial parameter of interest (τ in Equation 1) by maximising the likelihood function in the presence of missing data. We will not supplement this analysis with a separate approach, usually multiple imputation, MI, analysis, as the results of the two have been shown recently to be broadly equivalent (Lee & Shi, 2021). Additionally, in comparison to MI, FIML produces the same results every time, can be estimated in a single model and simulation studies show that it can reduce bias as well as MI (for a detailed discussion of FIML vs MI see Allison, 2012 or Jakobsen et al, 2017). The FIML approach only alleviates bias if pattern of missingness is dependent only on observed variables, namely missing at random (MAR); if the reason for missingness is due to unobserved variables, namely missing not at random (MNAR), then FIML or MI will not improve estimates. Note, however, that MAR and MNAR are not distinguishable based on observed data. If it seems likely data could be MNAR, sensitivity analysis will be conducted and reported alongside headline estimates.

¹¹ There is a convention in some disciplines that a 10pp (or larger) difference in treatment and control means at baseline constitutes 'imbalance' is thus justification for including those measures in sensitivity analyses, but there are counter-arguments to this idea. See Roberts, C. and Torgerson, D. (1999) 'Baseline imbalance in randomised controlled trials', *BMJ*, 319:185; de Boer et al. (2015) 'Testing for baseline differences in randomized controlled trials: an unhealthy research behavior that is hard to eradicate', *International Journal of Behavioral Nutrition and Physical Activity*, 12:4.

The FIML approach will be implemented using the `sem` command in Stata.¹²

Compliance

As the ITT approach captures the averaged effect of *offering* the intervention, we also propose to look at treatment effects in the presence of compliance at the pupil level to capture the average effect of *participation* in IWM+A.

For the purpose of this evaluation, we are employing the EEF's definition of compliance as 'the extent to which the critical ingredients of the intervention are delivered to and/or received by the target participants' (EEF, 2019b). In collaboration with the EEF and the delivery team at University of Oxford, we have defined 'compliance' as pupil attendance at sessions, which will be collected by TAs using attendance logs using a template developed by the delivery team. TAs will be asked to share the logs with the evaluator after all sessions have been completed. As shown in Table 5, children who have attended all five WM sessions and at least four arithmetic sessions will be marked as compliant; all those that do not obtain this will be marked as non-compliant. This is in line with the expectations set-out by the project team.

Table 5. Pupil level compliance measure

Compliance criterion	Data source	Compliance indicator
Attendance at WM sessions	Register of pupil attendance recorded by TAs	Pupil has attended all five WM sessions
Attendance at arithmetic sessions	Register of pupil attendance recorded by TAs	Pupil has attended at least four out of five arithmetic sessions

There will be two strands to the compliance analysis based on the measure outlined in Table 5. The core component of the compliance analysis will take compliance as a binary measure (where 1=compliant; 0=non-compliant, as defined Table 5), defined at the pupil level, based on attendance as recorded by the TAs. In a situation of imperfect compliance, whereby not all participating pupils are deemed compliant using the criteria outlined in Table 5, we will undertake a complier average causal effect (CACE) analysis, by drawing on an instrumental variable (IV) approach, and using a two-stage least squares (2SLS) estimation approach to recover the treatment effect for those who complied with assignment. The first stage of this approach estimates the extent to which the assignment to IWM+A encourages pupils to take up the treatment (the first stage regresses treatment assignment on compliance). This will estimate a compliance rate. Results for the first stage will report the correlation between the instrument and the endogenous variable; and an F test. The second stage of the IV estimation predicts the outcome as per Equation (1), but substitutes the treatment indicator ($IWMA_{i,t}$ in Equation (1)) with the compliance rate estimated in the first regression (Angrist & Krueger, 1991; Angrist, 2006). The results of this model will answer the research question: To what extent does *compliance with IWM+A* implementation requirements lead to improved outcomes for pupils? This model will be estimated for the primary outcome measure only.

We are also interested in understanding the role that 'dosage' (i.e. the amount of the intervention received by pupils) has on outcomes, given the important role programme participation can have on variance in outcomes, particularly for younger children (Zhi et al., 2010). If, as measured by the binary compliance indicator described above, the non-compliance rate exceeds 10%, we therefore propose as a second additional component to the compliance analysis to include data from pupil attendance records as a more detailed categorical variable when analysing the impact of IWMA+ on the primary outcome. This variable would take on one of eleven potential categories, from 0 (indicating the pupil has not attended any IWMA+ sessions) to 10 (indicating that the pupil has attended all five WM sessions and all five arithmetic sessions) with one-unit increments. The same analytical approach will be implemented using this more detailed dosage indicator as outlined for the core compliance model above (i.e. CACE analysis drawing on an IV approach and using 2SLS estimation). This will be an additional

¹² For more information on implementing missing data analysis using the FIML approach in Stata with the `sem` command, see here <https://www.stata.com/meeting/switzerland16/slides/medeiros-switzerland16.pdf>

analysis that will sit alongside the main component of the compliance analysis to better understand how different levels of session attendance affects outcomes. As with the core compliance model, this model will be estimated for the primary outcome measure only.

The limitation to estimating a dosage-varying local average treatment effect is that no differentiation is made between compliance with working memory sessions and compliance with arithmetic sessions. That is, a student who attends five working memory sessions and no arithmetic sessions would be treated identically to a student who attends five arithmetic sessions and no working memory sessions. Whilst we recognise this limitation, we believe dosage-varying effects may be justified for exploratory analysis under a situation where there is a large degree of non-compliance (over 10%), as it seems likely that any one-on-one time with a TA, on either the arithmetic or working memory component, could improve the primary outcome and thus be partially substitutable.

Intra-cluster correlations (ICCs)

The ICC is a key parameter for clustered trials. It represents the proportion of variance in a given outcome that can be explained by the variation between clusters (i.e. schools) as opposed to within-clusters.

The ICC used for the power calculations reported in the section on Sample size and power calculations overview and at protocol stage (see the [IWM+A evaluation protocol](#) for more information) is based on the ICC reported at analysis stage in the [previous EEF IWM efficacy trial](#), at 0.16.

In the final report we will report ICCs as at protocol stage; as at randomisation; and at analysis stage. The ICC at analysis stage will be based on the primary outcome measure; and will be calculated using: (i) the same model as Equation (1) and; (ii) a model similar to that documented in Equation (1) but with no covariates, accounting for the clustering of pupils in schools (the so-called empty model). ICCs will be estimated using Stata's `estat icc` command.

Effect size calculation

We will use the effect sizes (hereafter ES) for cluster-randomised trials given in the EEF evaluator guidance, as adapted from Hedges (2007):

$$ES = \frac{(\bar{Y}_T - \bar{Y}_C)_{adjusted}}{\sqrt{\sigma_S^2 + \sigma_{error}^2}}$$

Where $(\bar{Y}_T - \bar{Y}_C)_{adjusted}$ is the mean difference between the intervention and control group adjusted for baseline characteristics and $\sqrt{\sigma_S^2 + \sigma_{error}^2}$ is an estimate of the population standard deviation (variance).

From the primary outcome model, we will take each group's adjusted mean and variance to calculate the effect size. This variance will be the total variance (across both pupil and school levels, without any covariates, as emerging from a 'null' or 'empty' multi-level model with no predictors). The ES therefore represents the proportion of the population standard deviation attributable to the intervention (Hutchinson & Styles, 2010). A 95% CI for the ES, that takes into account the clustering of pupils in schools, will also be reported. Effect sizes will be calculated for each of the models estimated.

All ES will be estimated using the `eefanalytics` Stata package.¹³

¹³ See here for more information <https://ideas.repec.org/c/boc/bocode/s458904.html>

References

- Allison, P. D. (2012). Handling missing data by maximum likelihood. *SAS global forum*, 2012 (312), 1038-21.

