Attention and behaviour outcomes will be measured using the SNAP-IV Teacher Attention Rating Scale. As outlined in the theory of change (see Figure 1 in the IWM+A protocol), attention in class is considered to be an important proximal outcome leading to improved impact in maths. Further details on this measure can be found under Baseline measures.

The scale needs to be completed by an individual (i.e. a teacher) who is familiar with the pupil and their behaviour, and as such will be completed by pupils' teachers, who will consequently not be blind to allocation. Teachers will be asked to complete these measures for all nominated pupils in May 2022.

Sample size and power calculations overview

The initial power calculations in the Protocol (Brown et al., 2021) were based on both the information provided in the Invitation to Tender and the subsequent set-up meetings with the Delivery team and the EEF. Power and minimum detectable effect size (MDES) calculations were performed using the PowerUp! Tool (Dong & Maynard, 2013).

At protocol stage, upper and lower bound MDESs were calculated using a two-level random assignment assuming equal allocation to the intervention and control groups. The upper bound MDES calculations were based on assumed sample sizes of 240 schools equally allocated across intervention and control, with 10 pupils entered into the trial per school. The lower bound MDES calculation assumed sample sizes of 200 schools again equally allocated across treatment and control, with 10 pupils entered into the trial per school.

Based on the efficacy trial, we assumed the proportion of variance in level 1 outcomes explained by level 1 covariates R^2 was 0.25, equating to a pre-post-test correlation of 0.5, as per Table 3 (Wright et al., 2019).⁴ We used two-level clustered designs and based our calculations on an intra-cluster correlation (ICC) of 16 per cent (0.16, as per Table 3).

Assuming a desired power of 80 per cent, alpha of 5 per cent, a continuous, normally distributed outcome as well as taking all other assumptions outlined above and in Table 3, the overall upper bound MDES calculation at protocol stage was $d=0.172$, while the lower bound MDES calculation was $d=0.188$. Using the same parameters and assuming that on average 3 FSM-eligible pupils per school would be entered into the trial (a rate of 30% FSM-eligibility), the upper bound MDES at protocol stage was $d=0.221$ while the lower bound MDES was $d=0.242$.

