Table 3. Power Calculations

		Protocol				Randomisation	
		UPPER		LOWER		OVERALL	FSM
		OVERALL	FSM	OVERALL	FSM		
Minimum Detectable Effect Size (MDES)		0.172	0.221	0.188	0.242	0.188	0.231
Pre-test/post-test correlations	level 1 (pupil)	0.50	0.50	0.50	0.50	0.50	0.50
	level 2 (class)	NA	NA	NA	NA	NA	NA
	level 3 (school)	0	0	0	0	0	0
	level 2 (class)	NA	NA	NA	NA	NA	NA

⁴ It should be noted that the efficacy trial used KS1 arithmetic scores as baseline, as opposed to EYFSP suggested here. This was used as the assumption for the correlation in the power calculations as there is no currently published data on EYFSP and BAS3 correlations.

		Protocol				Randomisation	
		UPPER		LOWER		OVERALL	FSM
		OVERALL	FSM	OVERALL	FSM		
Intracluster correlations (ICCs)	level 3 (school)	0.16	0.16	0.16	0.16	0.16	0.16
Alpha		0.05	0.05	0.05	0.05	0.05	0.05
Power		0.8	0.8	0.8	0.8	0.8	0.8
One-sided or two-sided?		Two	Two	Two	Two	Two	Two
Average cluster size		10	3	10	3	10	4
Number of schools	intervention	120	120	100	100	100	94
	control	120	120	100	100	101	95
	total	240	240	200	200	201	189
Number of pupils	intervention	1,200	360	1,000	300	992	403
	control	1,200	360	1,000	300	1,004	401
	total	2,400	720	2,000	600	1,996	804

At randomisation stage, there were 201 schools and a total of 1,996 pupils with baseline data. This represents an average of 9.93 (10) pupils per school. Assuming the same parameters as at protocol stage and given the achieved overall sample, the MDES is $d=0.188$. As such, the MDES for the overall sample as reported in the SAP is the same as the lower bound MDES as reported at protocol stage ($d=0.188$).

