As also shown in Table 3, the number of schools with at least one FSM-eligible pupil at randomisation stage was 189 out of the 201 schools, with a total of 804 FSM pupils in the sample almost equally balanced across the intervention and control group (403 and 401 FSM pupils respectively). This represents an average of 4.25 (4) FSM pupils per school. Assuming the same parameters as at protocol stage and given the achieved sample of FSM pupils, the estimated MDES is $d=0.231$. This is roughly at the mid-point between the lower bound MDES for the FSM sample as estimated ($d=0.242$) and the upper bound MDES estimate ($d=0.221$) at protocol stage. This is likely due to the slightly higher rate of FSM eligibility (40.3%) as compared to the estimation at protocol stage (30%), despite the overall sample size aligning more with the lower bound MDES scenario. As such, the study should be powered to detect any meaningful difference for the FSM subgroup.

We acknowledge that the pre-post-test correlation is likely to be an overestimate, however, as there are no published correlations between BAS3 and EYFSP we have used data from the previous trial. To provide a more conservative estimate we have also run the power calculations with the assumption that there is no correlation. If the EYFSP is not correlated with outcome measures (i.e., pre-post-test correlation is equal to 0), the study will still be powered to detect an effect of 0.196 on all pupils, and 0.249 on FSM pupils.

Analysis

Primary outcome analysis

RQ1: What is the difference in number skills measured by the number skills subtest of the British Ability Scales (BAS3) of pupils in schools receiving IWM+A in comparison to those pupils in control schools receiving business as usual?

To address RQ1 this evaluation will use the age-standardised scores on BAS3 as a primary outcome for number skills, with prior attainment being accounted for by EYFSP scores (see Of the 201 schools that were randomised on 29th September 2021 as above, 195 nominated and provided baseline data for all ten selected pupils. Of the 6 schools not providing full data prior to randomisation, 4 schools had nominated and provided baseline data for nine out of ten pupils, while one school did so for six out of ten pupils and the final remaining school did so for four out of ten pupils. Thus, at baseline, the effective sample size was 1,996 pupils out of a theoretical population of 2,010 (201 schools multiplied by ten nominated pupils).

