Outcome measures section for more detail on the BAS3 and EYSFP). The pupil level BAS3 scores will be age-standardised with a mean of 100 and standard deviation of 15.

To address the primary research question an intention-to-treat (ITT) analysis will be undertaken using multi-level modelling (MLM) with fixed effects and random intercept. In ITT, data is analysed according to the group randomised, regardless of whether the treatment was actually received as intended, and irrespective of withdrawal from the intervention post-randomisation, or deviations in programme implementation. This principle is key in ensuring an unbiased analysis of intervention effects and is in line with the EEF's guidance (see EEF 2018).

To account for the nested nature of the data, a hierarchical linear model with two levels (school, pupil) will be fitted controlling for pre-intervention scores at the pupil level. Following the stratified randomisation, the model will include a term identifying the regions (strata).

Impact will be estimated by fitting the model in equation (1). Equation (1) is known as a 'random intercepts' model because $\beta_{0j} = \beta_0 + u_j$ is interpreted as the school-specific intercept for school j and $\beta_{0j} \sim i.i.d. N(\beta_0, \sigma_u^2)$ is random (it is a number that can take any value):

$$(1) \quad Y_{ij} = \beta_0 + IWMA_j \tau + Z_j \beta_1 + X_{ij} \beta_2 + u_j + e_{ij}$$

Where:

Y_{ij} = BAS3 scores on the number skills subtest for child i in school j ;

β_0 = the cluster-level coefficient for the slope of a predictor on number skills;

$IWMA_j$ = a binary indicator of the school assignment to intervention [1] or control [0];

Z_j = school-level characteristics i.e. the stratifying variable of geographical location (as used for randomisation);

X_{ij} = pupil level characteristics for pupil i in school j , i.e. the pre-intervention EYFSP score;

u_j = school-level residuals and

e_{ij} = individual-level residuals.

The coefficient τ in Equation 1 above will represent the outcome of the trial, with respect to the primary outcome measure. Equation 1 will also be replicated for each of the three secondary outcome measures (see next section).

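### Equation (1) gives EYFSP a single pupil-level slope; pre-specifying the school mean EYFSP as a second term may improve precision at almost no cost, by an amount the SAP's figures cannot fix

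*SAP*

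**What the plan says.** In the SAP's Primary outcome analysis, "a hierarchical linear model with two levels (school, pupil) will be fitted controlling for pre-intervention scores at the pupil level". In Equation (1) the school-level vector holds only the region stratum, and the pupil-level vector holds only the EYFSP score, with one coefficient. No school mean of EYFSP appears. Secondary outcome analysis carries this model to Wider Maths and Working Memory, and Subgroup analyses carries it to FSM with an interaction term. Attention and Behaviour uses its own SNAP-IV baseline and is not affected.

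Under Baseline measures, EYFSP is the sum of two practitioner ratings from Reception, ranging from 2 to 6. The SAP says openly that it is not sensitive, because of its restricted range.

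In the Sample size and power calculations overview, "the proportion of variance in level 1 outcomes explained by level 1 covariates R^2 was 0.25", corresponding to a correlation of 0.5. Table 3 sets the school-level correlation to zero throughout: "level 3 (school) 0 0 0 0 0 0". The SAP calls 0.5 a likely overestimate and adds that with no correlation "the study will still be powered to detect an effect of 0.196 on all pupils, and 0.249 on FSM pupils".

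**The concern.** In a school-randomised trial with about ten pupils per school, most of the uncertainty in the treatment effect comes from differences between schools. A baseline helps most when it explains those differences. A random-intercept model with one EYFSP slope estimates that slope mainly from contrasts between pupils in the same school, then applies it to differences between schools as well. If a coarse score attenuates the within-school slope, and averaging up to ten pupils removes some of that noise, the between-school slope could be steeper. The common slope would then under-adjust for school differences.

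What is at stake is precision in the primary model and in the other models that use EYFSP. More schools cannot be added after randomisation, whereas the school mean comes from data the evaluators will already hold. The term has to be specified before outcomes are seen; added later it would be a discretionary choice.

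**Working it through.** **Inputs (SAP, Sample size and power calculations overview and Table 3).** "Assuming a desired power of 80 per cent, alpha of 5 per cent"; the Table 3 row "One-sided or two-sided" reads two-sided; "based our calculations on an intra-cluster correlation (ICC) of 16 per cent"; pupil-level R² 0.25; school-level R² 0; J = 201 schools allocated 1:1; n = 9.93 pupils per school, entered as 10.

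**1. Reproduce the SAP's figures.** For a two-level cluster-randomised design,

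MDES = M × √{[ICC(1 − R²_school) + (1 − ICC)(1 − R²_pupil)/n] / (0.25 J)},

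with M = t(0.975; 199) + t(0.80; 199) = 1.972 + 0.843 = 2.815.

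- r = 0.5: 0.16 + 0.84 × 0.75/10 = 0.223; MDES = 2.815 × √(0.223/50.25) = 0.188, as stated.
- r = 0: 0.16 + 0.84/10 = 0.244; MDES = 2.815 × √(0.244/50.25) = 0.196, as stated.

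The FSM figures (0.231, and 0.249 with no correlation) and the four protocol columns also reproduce.

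**2. Where the variance lies.** With the pupil baseline, the between-school share is 0.16/0.223 = 72%. On these inputs the baseline lowers the variance by 1 − 0.223/0.244 = 8.6%, and the MDES by about 4%.

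**3. How one slope is weighted.** The random-intercept fit down-weights the school-mean contrast by θ = σ²_e/(σ²_e + nσ²_u). This is 0.63/(0.63 + 1.6) = 0.28 with pupil R² 0.25, and 0.84/(0.84 + 1.6) = 0.34 with none. For an assumed EYFSP ICC of 0.05 to 0.20, the between-school contrast gets about 5% to 12% of the weight in the common slope. At the low end, 0.28 × 10 × (0.05 + 0.95/10) = 0.41 against 9 × 0.95 = 8.55, or about 5%. At the high end, 0.34 × 10 × (0.20 + 0.80/10) = 0.95 against 9 × 0.80 = 7.20, or about 12%. The fitted slope is essentially the within-school one.

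**4. Ceiling on the gain.** Keep pupil R² at 0.25 and let school-level R² vary (assumed values, since the SAP gives none):

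| School-level R² | Variance term | MDES |
|---|---|---|
| 0 | 0.223 | 0.188 |
| 0.10 | 0.144 + 0.063 = 0.207 | 0.181 |
| 0.20 | 0.128 + 0.063 = 0.191 | 0.174 |
| 0.30 | 0.112 + 0.063 = 0.175 | 0.166 |

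The reference here is the planning value of zero, not Equation (1). An uncentred pupil score already explains some school variance, so these falls are an upper limit on what the extra term adds.

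**5. Like-for-like comparison with Equation (1).** A simulation used 200 schools of 10 pupils, outcome ICC 0.16 and 400 runs per scenario, with all models fitted to the same data. EYFSP ICC and slopes are assumed. Entries are the standard deviation of the estimated effect.

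| EYFSP ICC; slope within / between | Pupil score only | Plus school mean | Further cut |
|---|---|---|---|
| 0.10; 0.5 / 0.5 | 0.0652 | 0.0652 | 0% |
| 0.10; 0.5 / 0.9 | 0.0572 | 0.0568 | 0.7% |
| 0.15; 0.5 / 0.25 | 0.0647 | 0.0642 | 0.8% |
| 0.15; 0.3 / 0.8 | 0.0597 | 0.0578 | 3.2% |
| 0.10; 0.3 / 0.9 | 0.0617 | 0.0577 | 6.5% |

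**6. Closer to this trial's pupils.** Further simulations took a coarse score and low attainers chosen by noisy teacher judgement, again with assumed parameters. At outcome ICCs of about 0.12 to 0.17 the further cut was about 0% to 10%. It was near nil when rating leniency varied strongly between schools, and there was never a material loss. At realised ICCs of 0.19 to 0.25 the cut was 1.6% to 11%.

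Two examples from the latter set (no baseline / Equation (1) / plus mean):

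- 0.0732 / 0.0695 / 0.0662. Since (0.0695/0.0662)² = 1.102, the added term is worth about 20 schools in 201.
- 0.0741 / 0.0709 / 0.0698. Since (0.0709/0.0698)² = 1.032, it is worth about 6.

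**The case against.** The strongest reply is that nothing in the SAP is wrong here. Equation (1) gives an unbiased estimate with valid inference, the SAP is candid about EYFSP's weakness, and it reports the MDES with no correlation. That stands in full.

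A reader might infer from the small move between 0.196 and 0.188 that Equation (1) leaves the between-school information in EYFSP mostly unused. The SAP does not support that. The small move follows from Table 3's zero school-level correlation, which is a planning input and not a property of the model. The score is not stated to be school-centred, so it carries school differences into the fit. In the equal-slope simulation (EYFSP ICC 0.10), the pupil score alone cut residual school variance from 0.156 to 0.132, and adding the mean gave 0.131. In the two examples at the end of the working, Equation (1) already delivers 0.0037 of the 0.0070 total reduction (53%) and 0.0032 of 0.0043 (74%).

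A reader might also infer that the school mean would certainly lower the standard error, or would bring the MDES to 0.174 or so. Neither follows. The term helps beyond Equation (1) only if the two slopes differ, and the SAP gives neither slope, no EYFSP ICC and no school-level correlation. The direction is open too: averaging reduces pupil-level noise, but practitioners' rating standards may differ between schools, and the mean is taken over selected low attainers.

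What remains is the asymmetry: a possible gain against a cost of about one school-level degree of freedom.

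**Conclusion.** The point holds as an optional efficiency improvement of uncertain size. Equation (1) imposes equal slopes where the SAP gives some reason to doubt equality, and on its planning inputs 72% of the variance of the effect lies between schools. The further reduction in standard error over Equation (1) ranges from about 0% (equal slopes, or large differences in rating standards between schools) to roughly 10%. All of these figures rest on assumed slopes, EYFSP ICCs and selection behaviour. The MDES values of 0.181, 0.174 and 0.166 are a ceiling and should not be quoted as the expected benefit. This is neither an error nor a source of bias.

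**What to change.** In Equation (1), for the primary, FSM, Wider Maths and Working Memory models, add the school mean EYFSP alongside the pupil's own score, with its own coefficient. Define the mean over all pupils nominated before randomisation who have a numeric EYFSP score. Exclude code A and missing values from the mean, and include pupils whether or not they have endline data. That last condition matters: a mean over analysed pupils only would depend on attrition after randomisation and would no longer be a pure baseline quantity. For FSM, use the mean over all nominated pupils, since that model keeps the whole sample.

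The coefficient τ remains the quantity of interest. The effect size is unaffected in definition, because its denominator is the variance from the empty model. The cost is one derived variable from NPD data already planned for, about one school-level degree of freedom out of roughly 190, and a few lines of SAP text settled before outcome data are seen.
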